Title of Project: ***Use of mHealth Technology for Supporting Symptom Management in Underserved Persons Living with HIV***

IRB: AAAP1258

NCT: NCT02897141

Principal Investigator and Team Members:

Principal Investigator: **[name], PhD**

Co-Investigators: [name] PhD, [name] MD, [name]

Organization: The Trustees of Columbia University in the City of New York

Grant Award Number: **R21HS23963**

Date Document Last Edited: 6/17/18

Protocol: AAAP1258 Abbreviated Title: mVIP Principal Investigator: [name]

Title: Use of mHealth Technology for Supporting Symptom Management in Underserved Persons Living with HIV

STUDY PURPOSE AND RATIONALE:

HIV has changed from an acute illness to a chronic disease. The success of HIV medications and treatments has significantly altered the course of the disease. While AIDS-related illnesses are no longer the primary threat, a new set of HIV-associated complications have emerged, resulting in a chronic disease that for many will span several decades of life. The ability to self-manage adverse symptoms of HIV illness has been shown to improve patient-centered outcomes. In response to this need a team at UCSF developed a paper-based symptom management manual with self-management strategies for 21 common HIV/AIDS adverse symptoms (PCOR evidence). The efficacy of the manual was demonstrated in a 775-person RCT over three months at 12 sites. However, subsequent use of these strategies has been very limited; mHealth offers an ideal platform for the implementation and dissemination of evidence-based strategies for HIV symptom management. Due to the high incidence of HIV among racial and ethnic minority populations, it is appropriate to develop mHealth tools tailored to the needs of these populations. mHealth technology has the potential to address many of the healthcare needs of persons living with HIV/AIDS (PLWH) including symptom management. In response to these current issues, our proposal seeks to inform the development and testing of a mHealth application that will incorporate findings from PCOR studies to improve the outcomes of PLWH.

To improve outcomes for those most in need, our study activities are focused on communities with the greatest burden of HIV in the US, including racial and ethnic minorities and those of low socioeconomic status.

The goal of this study is to facilitate the dissemination and implementation of PCOR using mHealth technology to improve self-management of adverse symptoms in persons living with HIV/AIDS (PLWH). Symptom management in PLWH is especially important because the US HIV epidemic continues to exact a huge toll, especially among AHRQ priority populations including racial, ethnic, and sexual minorities and low-income persons. The incorporation of HIV symptom management strategies into patient's lives through the use of mHealth technologies has the potential to advance the effective dissemination and implementation of PCOR finding. The overall research question is to test the efficacy of the mVIP app which will be created as part of this study.

SPECIFIC AIMS

- 1) Apply participatory design, heuristic evaluation, and end-user usability testing (using eye tracking software) and think-aloud protocol method to incorporate PCOR evidence for HIV symptom management into a mobile health application (mVIP) for use in patient self-management.
- 2) Using a randomized design, examine the effect of mVIP as compared to an attention control group on primary outcomes of symptom frequency and intensity.
Hypothesis: Study participants who use the mVIP system to access symptom strategies are more likely to have decreased symptom frequency and intensity at the end of 12 weeks.
- 3) Guided by the PRECEDE-PROCEED model of health program planning and evaluation,

examine PLWH's perceptions of the predisposing, enabling, and reinforcing factors for mVIP use.

Overview of Design, Methods, Target/Accrual Enrollment, Recruitment/Enrollment Status				
Aim	Design/Methods	Target Enrollment	Enrolled/Accrued	Enrollment Status
1	A) Participatory design using card sorting activity	40	31	Closed to further enrollment. Study-related procedures ongoing.
	B) heuristic evaluation	5	5	Closed to further enrollment. Study-related procedures ongoing.
	C)End-user usability testing Utilizing eye tracking software and think-aloud protocol	20	20	Closed to further enrollment. Study-related procedures ongoing.
2	Randomized controlled design	80 (Intervention:40, control: 40)	80	Closed to further enrollment. Study-related procedures ongoing.
3	Descriptive: focus groups/in-depth interviews	Focus groups: 40 In-depth interviews: 12	0	Closed to further enrollment. Study-related procedures ongoing.

Subject Population: We anticipate two categories of research subjects in our study:

- 1) Persons living with HIV/AIDS
- 2) Experts in human computer interaction.

Setting and Sample

Eligibility Criteria (Aim 1a): In order to participate in Aim 1a of this study, participants must be:

- 1) Diagnosed with HIV/AIDS
- 2) Over the age of 18 years
- 3) Able to provide written informed consent
- 4) Able to communicate in English
- 5) Report at least 2 HIV related adverse symptoms in the past week
- 6) Cognitive state (as assessed by a modified version of the standard Mini Mental State Exam (MMSE): total score of 3 or higher)

This process, which is an accepted and necessary component prior to final mVIP implementation, will include an electronic survey. After survey completion we will conduct a card sorting exercise utilizing a

think –aloud protocol in which the participants will be presented with a stack of cards, representing the content of mVIP app, while they are encouraged to share their insights with us and sort/group the cards in a way that would make sense to them.

Data Analysis: A hierarchy analysis will be conducted for establishing the rank order of symptoms and self-management strategies.

Eligibility Criteria (Aim 1b): Five informaticians will participate as usability experts.

Study participants must be at least a masters-level prepared in human computer interaction, clinical informatics or public health informatics.

Each usability expert will be asked to evaluate the system using the Heuristic Evaluation Checklist and to think-aloud while performing the usability testing. The process will be recorded using Morae software™, which allows the researcher to record and analyze the audio recording and screen shots that are captured during the heuristic evaluation.

Data Analysis: At the end of this evaluation, the frequencies of usability issues will be calculated according to Nielsen's heuristic principles. Following the heuristic evaluation, the mVIP app will be refined.

Eligibility Criteria (Aim 1c):

- 1) Diagnosed with HIV/AIDS
- 2) Over the age of 18 years
- 3) Able to provide written informed consent
- 4) Able to communicate in English
- 5) Report at least 2 HIV related adverse symptoms in the past week
- 6) Be the owner of a smartphone and/or tablet.
- 7) Cognitive state (as assessed by a modified version of the standard Mini Mental State Exam (MMSE): total score of 3 or higher)

For end-user usability testing, we will conduct end-user usability testing on 10 Android smartphone users and 10 OS smartphone users.

Data Analysis: The analysis will be based on the Tobii recordings of user sessions including voice/screen and eye movement/fixation, transcriptions, notes, and the user surveys. Mean task performance time will be calculated. Critical incidents characterized by comments, silence, and repetitive actions will be identified with eye movement. We will review these incidents in detail using Tobii Eye-tracking software. The incidents identified and the users' written comments will be summarized. Eye-tracking analysis, and content analysis, a technique for making objective, replicative and valid inferences from data, will be performed.

Eligibility Criteria (Aim 2)

- 1) Diagnosed with HIV/AIDS
- 2) Over the age of 18 years
- 3) Able to provide written informed consent
- 4) Able to communicate in English
- 5) Report at least 2 HIV related adverse symptoms in the past week
- 6) Be the owner of a smartphone and/or tablet.
- 7) Cognitive state (as assessed by a modified version of the standard Mini Mental State Exam (MMSE): total score of 3 or higher)

Aim 2: Using a randomized design, examine the effect of mVIP as compared to an attention control group on primary outcomes of symptom frequency and intensity. We will conduct a 12 week trial of the mVIP. We will recruit 80 HIV+ persons with the proposed sample size of 40 in each of the following two groups:

- 1) Intervention group: mVIP app with access to symptom strategies
- 2) Control group: mVIP app without access to symptom strategies

The symptom frequency and intensity will be compared between the two groups aiming to test the effectiveness of improvement in symptom intensity score for the mVIP group over the control group.

Randomization: Patients will be randomized (1:1) to mVIP or an attention control group. Both groups will receive the mVIP app on their smartphones. The allocation sequence of participants will be concealed from the research assistant who will be responsible for randomizing study participants. This will be a single-blinded study and control group participants will not have access to the symptom strategies. We had initially planned to give a smartphone to each study participant as a compensation. However, during the first aim of our study, we learned that many of our study participants already have smartphones. For those who do not, the learning process for the basic use of a smartphone, in addition to the training needed to use our intervention, will be too difficult. Thus, we have decided to change the initial compensation plan. Instead, we will be giving our participants a token of appreciation for their participation in the study. Both groups will report their symptoms on their smartphone app every week. Participants in the mVIP (intervention) group will receive targeted symptom strategies from the UCSF symptom management manual (PCOR evidence) based on the symptoms that they report.

Contact information will be retained and used by study staff to remind participants about their follow up appointments. Contact information will be kept in a separate database from research data.

Eligibility Criteria (Aim 3):

For Aim 3: They must have participated in AIM 2

PROCEDURES

Aim 1: Participatory Design, Heuristic Evaluation and End-User Usability Testing.

During the initial stages of designing a mVIP health management app Inclusion of stakeholders throughout the app design process is vital to ensure that patient needs unknown to the investigators are taken into account. This process, which is an accepted and necessary component prior to final mVIP implementation.

Aim 1a) Participatory Design: Participants will complete an electronic survey, on site, containing demographic questions, technology use, medication adherence, and health-related quality of life. Upon survey completion they will be asked to perform a card sorting exercise/think aloud protocol. They will be presented with a stack of cards that represent the content and functionality for the mVIP app. They will be encouraged to try and sort the cards into groups that make sense to them and share their insights with our team.

Aim 1b) Heuristic Evaluation: Five informaticians will participate as usability experts. Study participants must be at least a masters-level prepared in human computer interaction, clinical informatics or public health informatics. The usability experts will be provided with a prototype of mVIP. Each usability expert will be asked to evaluate the system using the Heuristic Evaluation Checklist and to think-aloud while performing the usability testing. The process will be recorded using Morae software™ (Techsmith Corporation, Okemos, MI) (102), which allows the researcher to record and analyze the audio recording and screen shots that are captured during the heuristic evaluation. At the end of the evaluation, each expert will be compensated \$150. Each heuristic will be evaluated by one or more items and the overall severity of the identified heuristic violations will be rated.

Data Analysis: The frequencies of usability issues will be calculated according to Nielsen's heuristic principles.

Following the heuristic evaluation, we will refine the mVIP.

Once the mVIP prototype is refined and implemented by the programmer, we will conduct an evaluation: Aim 1c) End- User Usability Testing.

Aim 1c) End-User Usability Testing. Usability testing of a Beta version of mobile Video Information Provider (mVIP). We will be conducting usability testing of a Beta version of the mVIP app. The purpose of the usability testing is to improve the effectiveness, efficiency and user satisfaction of the mVIP app. To achieve this goal, we will be using eye-tracking and think-aloud method to examine the end-user task performance to assess mVIP system validation and human- communication interaction (HCI) in a laboratory setting. We will recruit 20 persons living with HIV (PLWH) (10 PLWH for the usability testing on Android smartphones and 10 PLWH for the usability testing on iPhones. All participants will be provided with scenarios and asked to complete tasks using mVIP system on a smartphone. While they are doing the tasks, their eye movements and smartphones screen will be recorded using Tobii Pro Eye-tracker. During each task, the start and stop times of tasks will be also measured. After completing the tasks, they will be asked to think aloud and verbalize their thoughts about the tasks they completed, through a replay of the screen recordings. Participant's reactions and verbal comments will be video and audio recorded. As part of the usability assessment, participants will complete electronic surveys containing demographic questions, health literacy, technology use, medication adherence, and health-related quality of life.

Aim 2) Randomized controlled design: Examine the effect of mVIP intervention as compared to an attention control group on primary outcomes of symptom frequency and intensity.

We will recruit 80 PLWH to participate in a 12 week trial. The sample size and statistical power calculation is based on the hypothesis test of improvement of the symptom frequency and intensity after the implementation of the mVIP system. The effect size is based on our 12 week feasibility study with 42 participants. The criterion for significance (alpha) has been set at 0.05 for the two- sided test. We will recruit 80 HIV+ persons with the proposed sample size of 40 in each of the two groups (assuming a 1:1 allocation ratio). To account for a potential attrition rate of 20%, we propose to achieve a final sample of 64 patients (32 per group). Additionally, each patient will have 20% chance to miss any one of the symptom reporting opportunities between week 2 and week 10.

For the symptom frequency outcomes, this study will have 87.9% power to detect 20% decrease in symptom frequency (for example, from an average 8 symptoms to average 6.4 symptoms) from the

baseline to the end of study (i.e., 12th week). For the comparison between the mVIP group and the control group, this study will have 85.4% power to yield a statistically significant result (assuming an intention-to-treat principle for the analysis) to test 15% improvement in one group over another group (i.e., the mVIP group decreases 20% in symptom frequency and the control group decreases 20%+15%=35% in symptom frequency). For the symptom intensity outcomes, this study will have 96% power to detect decrease in symptom intensity score of a medium effect size of 0.6 from the baseline to the end of study. For the comparison of the two groups, this study will have about 95% power to yield a statistically significant result to test an effective size of 0.6 improvement in symptom intensity score for the mVIP group over the control group.

Following randomization of participants, both the intervention and control groups will receive the mVIP on their phones. All participants will complete all study-related questionnaires electronically on their smartphone. All subjects will complete a demographic questionnaire as well as the Newest Vital Sign instrument to measure health literacy at baseline in addition to the judgment of a team member that they are cognitively intact. Similar to our feasibility study, participants will use the system at least once every week and will receive a reminder email or phone call if they have not used the system in more than 1 week. Symptom frequency and intensity will be collected every week. The remainder of the measures will either be collected at weeks 0 and 12 or week 12 only. See the outcome measures table below for details.

Aim 3) In-Depth Interviews and Focus Groups to evaluate PLWH's perceptions of the predisposing, enabling, and reinforcing factors for mVIP use

In-Depth Interviews will be approximately 30 minutes in length and will occur immediately following a participant's follow up appointment. We will include a \$10 reimbursement for participants' time. After obtaining informed consent, study staff will audio record a structured interview aimed at collecting feedback on usage habits, potential technical or usability issues, and the session reminder structure. Each interview recording will be transcribed and transcripts will be analyzed independently for content by research team members.

The focus groups will be 60-90 minutes in length. We will include \$40 reimbursement for participants' time. Following completion of the informed consent process, all focus group sessions will be audio-recorded. The focus group guide will be informed by the Predisposing, Reinforcing, and Enabling Constructs in Evaluation (PRECEDE) portion of the PRECEDE-PROCEED Model of health program planning and evaluation. The integration of these frameworks for application in HIT implementation evaluation has been proposed by a number of authors as a strategy for assessing predisposing, enabling, and reinforcing factors for use and acceptance of HIT.

The team will adhere to qualitative research processes to ensure the credibility, confirmability, dependability and transferability of the qualitative data from these analyses. To support the credibility of the data, we will conduct peer debriefing and triangulate findings across multiple data sources (surveys, focus group data). In addition, we will use "member checks," i.e., sharing of initial data interpretations with participants, to ensure accurate interpretations. Triangulation of findings, along with reflexivity, will enhance the confirmability of the interpretations. The investigators will carefully record an audit trail and keep extensive field notes to facilitate transferability of study findings into

other contexts. Each focus group recording will be transcribed; transcripts will be analyzed independently for content by research team members.

Overview of Study Instruments

Please note that all study instruments for the trial are included as attachments entitled [mVIP Baseline](#)

[12-9-2016](#) and [mVIP Follow-up 12-2-2016](#)

Primary Outcome Measure: Change in HIV related symptom status as measured by the PROMIS-29.

Baseline Measures:

- Demographics
- PROMIS-29
- PROMIS-GI
- SF-12
- RAND-36
- Case adherence index and ART adherence VAS
- TOFLHA
- NVS
- Symptoms distress module
- Healthcare Provider Engagement
- Non-CPT/Study Medical and Other Services (CTN-0051)
- Health ITUES
- PSSUQ

Follow-up Measures:

- PROMIS-29
- PROMIS-GI
- SF-12
- RAND-36
- Case Adherence Index and ART adherence VAS
- Symptom distress module
- Healthcare Provider Engagement
- Non-CPT/Study Medical and Other Services (CTN-0051)
- Health ITUES
- PSSUQ

Data Analysis

The study analysis followed an intention-to-treat approach. Intervention and control characteristics collected at baseline were summarized with descriptive statistics (mean \pm SD or frequency). To assess the effect of the intervention on symptom burden during the follow-up period, we used linear mixed model to analyze repeated measured data, and the models controlled for age, sex, race, education and CD4 count.

For all secondary outcome measures, which were collected at baseline and 12 week follow-up, we used a same linear mixed model or a generalized linear mixed model. We used linear mixed model for continuous outcomes (e.g. PROMIS score); generalized linear mixed model (Poisson or Negative binomial model) for count outcomes (e.g. number of ER visits); the generalized linear mixed models (logistic model) for binary outcomes (e.g. CASE Adherence Index). All models were controlled for age, sex, race/ethnicity, education and CD4 count.

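### Are the 96% and about 95% power figures for symptom intensity wrong because their assumptions are not written down?

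*Combined protocol and SAP*

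**What the plan says.** The power statement is in the Procedures section under Aim 2, Randomized controlled design. It sets a two-sided alpha of 0.05, recruits 40 per arm, and expects 32 per arm after 20% attrition. It adds that "each patient will have 20% chance to miss any one of the symptom reporting opportunities between week 2 and week 10". On the source of the effect it says only this: "The effect size is based on our 12 week feasibility study with 42 participants".

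Two figures are given for symptom intensity. Within a group, "this study will have 96% power to detect decrease in symptom intensity score of a medium effect size of 0.6", measured from baseline to the end of the study. Between groups, "this study will have about 95% power to yield a statistically significant result to test an effective size of 0.6 improvement" for the app with strategies over the control app.

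Three other places bear on how to read these figures. The Aim 2 hypothesis in Specific Aims says users are "more likely to have decreased symptom frequency and intensity at the end of 12 weeks". The Aim 2 procedures state: "Symptom frequency and intensity will be collected every week". The Data Analysis section fits a linear mixed model to the repeated measurements under intention to treat, adjusted for age, sex, race, education and CD4 count. Its purpose is described this way: "To assess the effect of the intervention on symptom burden during the follow-up period".

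**The concern.** The between-group comparison is the only randomised test of symptom intensity, so its power carries the sample-size argument for that outcome. A reader who applies the obvious formula to the stated inputs gets 66% or 76%, about 20 to 30 points below the claim. A reader who looks for the missing inputs finds none: no test, no scale for the 0.6 (SD of the score or SD of the change), no correlation, no statement of which n was used, and no mean or SD from the feasibility study.

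The time contrast adds to the doubt. The hypothesis looks to week 12, while the model looks at the whole follow-up period, and power depends strongly on which is meant. If about 95% belonged to an average over follow-up but was read as power at week 12, the trial would seem better powered for its stated hypothesis than it is.

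**Working it through.** **Inputs from the plan:** effect 0.6; two-sided alpha 0.05; n = 40 recruited or 32 retained per arm; weekly reports; 20% chance of a missed report in weeks 2 to 10. **Assumed, because the plan gives no value:** within-patient correlation ρ, equal between all pairs of weeks. Power comes from the noncentral t distribution with noncentrality δ = 0.6/SE. Scores are in SD units.

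**1. The 96% within-group figure.** For a paired t-test with 0.6 in SDs of change, δ = 0.6√n.
- n = 40: δ = 0.6 × 6.325 = 3.795, 39 df, power 95.9%.
- n = 32: δ = 0.6 × 5.657 = 3.394, 31 df, power 90.8%.

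The stated figure is matched at n = 40. If 0.6 is in SDs of the raw score, the SD of change is √(2(1−ρ)). At ρ = 0.5 this equals 1, so the two scales coincide. With n = 32, the raw scale gives 96.0% at ρ = 0.608.

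**2. The between-group figure by the simplest test.** For an unadjusted two-sample t-test, δ = 0.6√(n/2).
- n = 32: δ = 2.400, power 65.6%.
- n = 40: δ = 2.683, power 75.5%.

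Neither is near 95%, so this was not the calculation used.

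**3. The between-group figure using the weekly reports.** For the mean of m = 12 weekly reports minus baseline, the variance per patient is (1 + (m−1)ρ)/m + 1 − 2ρ, and SE = √(2 × variance/n). No reports are missed here.
- n = 40, ρ = 0.5: variance = 6.5/12 + 0 = 0.5417; SE = 0.1646; δ = 3.646; power 95.0%.
- n = 32, ρ = 0.5: SE = 0.1840; δ = 3.261; power 89.4%.
- n = 32, ρ = 0.608: variance = 0.6407 − 0.216 = 0.4247; SE = 0.1629; δ = 3.683; power 95.2% (94.9% with the missed reports).

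**4. The between-group figure for a slope that reaches 0.6 at week 12.** With weeks 0 to 12 all observed, the squared deviations of the week numbers sum to 182, and the SE of the week-12 difference is 12√(2(1−ρ)/(182n)).
- n = 32, ρ = 0.5, nothing missed: SE = 0.157, δ = 3.816, power 96.4%.
- Same, with 20% of the week 2 to 10 reports missed (information averaged over simulated patterns): SE = 0.163, δ = 3.679, power 95.2%.

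**5. How far the choice of contrast moves the answer.** All rows use n = 32, ρ = 0.5 and the missed reports.

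| Between-group contrast | Power |
|---|---|
| Week 12, baseline-adjusted | 78% |
| Mean change over weeks 1–12 | 89% |
| Mean of weeks 1–12, no baseline | 89% |
| Slope reaching 0.6 at week 12 | 95% |
| Mean of weeks 1–12, baseline-adjusted | 99% |

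**Reading.** One conventional set of assumptions (n = 40, ρ = 0.5) gives 95.9% within group and 95.0% between groups, which matches both stated figures. A set that uses the retained n and the stated missed-report rate also gives about 95%, for a contrast expressed at week 12. The plan's text favours a repeated-measures calculation: a missed-report rate for weeks 2 to 10 has no bearing on a plain week-12 test, yet it stands in the sample-size paragraph.

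**The case for a change.** The strongest case for acting is that a power figure should identify its own basis, and this one does not. Several incompatible sets of assumptions give about 95%. The set in step 3 with 40 per arm ignores the attrition that the same section plans for. A baseline-adjusted comparison at week 12 alone, the most literal reading of the hypothesis, gives 70%, 73%, 78%, 84% and 91% at correlations of 0.3, 0.4, 0.5, 0.6 and 0.7 with 32 per arm. It needs a correlation of about 0.76 to reach 95%. Documenting the calculation would take one paragraph.

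Much of that stands as a remark on reporting. The test, the SD scale, the correlation, the n used and the between-group time contrast are indeed unstated, and the figures cannot be traced to a single source. It does not show an error. The within-group contrast is stated, both sample sizes are stated, and the 96% is matched at one of them. The week-12 test alone also sets aside the weekly data that the planned model uses, including the partial data of patients who drop out.

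**Conclusion.** This is a gap in documentation, and no change to the plan is needed. Neither figure is shown to be wrong: 96% is matched by a paired t-test at 40 patients (95.9%), and about 95% is reached by ordinary repeated-measures calculations (95.0% at 40 per arm, 95.2% at 32 per arm with missed reports, both at a correlation of 0.5). The low values of 66% and 76% come from a test that the plan does not propose.

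The conclusion rests on assumed correlations near 0.5 to 0.6 and an equal-correlation structure, and it leaves out the five planned covariates. It shows that the figures are attainable, not how the sponsor obtained them. A reader interested only in week 12 should bear in mind that power there may be nearer 78% than 95% if the correlation is 0.5.

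Further detail would alter nothing. The enrolment table shows the trial closed at 80, the Data Analysis section is already written in the past tense, and the precision of the result will be judged from its confidence interval, not from the planning power.

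### The models are not stated to use the outcome's baseline value, as a covariate or as a response with a mean common to both arms; unless that was done, precision is lost on the continuous outcomes

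*Combined protocol and SAP*

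**What the plan says.** Data Analysis names the adjustment terms twice. For symptom burden: "we used linear mixed model to analyze repeated measured data, and the models controlled for age, sex, race, education and CD4 count". For the secondary outcomes, "which were collected at baseline and 12 week follow-up, we used a same linear mixed model or a generalized linear mixed model", followed by "All models were controlled for age, sex, race/ethnicity, education and CD4 count". Neither list contains the outcome's baseline value. The fixed effects (group, time, interaction) are not written out, and no sentence says whether the baseline means are free or common to the arms.

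Baseline values do exist. Overview of Study Instruments gives "Primary Outcome Measure: Change in HIV related symptom status as measured by the PROMIS-29", and PROMIS-29 is on both the baseline and the follow-up list. Procedures, Aim 2 adds "Symptom frequency and intensity will be collected every week" and "The remainder of the measures will either be collected at weeks 0 and 12 or week 12 only". Allocation is randomised 1:1 (Randomization). The sample-size text in Procedures, Aim 2 plans 40 per group and expects 32 per group after 20% attrition.

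**The concern.** Leaving baseline out of a covariate list does not prove that it was unused. With only two visits, the data are repeated only if baseline is itself a response row. So for the week 0 and week 12 outcomes, PROMIS-29 among them, the text most naturally describes a group-by-time model with free baseline means. Its treatment contrast is the difference in change. For the weekly symptom reports, a model of follow-up values alone is also possible.

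Both give up precision. The change contrast spends information estimating a baseline group difference whose expectation randomisation has already set to zero. The follow-up-only model discards the baseline values. With 32 completers per group there is little precision to spare. The reader also cannot tell which contrast was tested.

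**Working it through.** **Inputs from the documents.** Two-sided alpha 0.05; 40 randomised and 32 completers per arm; between-group effect size 0.6 for symptom intensity, with power of about 95% (Procedures, Aim 2).

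**Assumed.** Unit SD at each visit. r, the baseline to week-12 correlation given the listed covariates, is shown at 0.3 / 0.5 / 0.7. The 0.6 is taken in endpoint SD, because no standardiser is given.

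**The plan's own figure.** A plain two-sample comparison has SE = sqrt(2/32) = 0.250. Power is Φ(0.6/0.250 − 1.96) = Φ(0.44) = 67% (66% by t), not 95%. With 32 per arm, 95% needs a variance factor of about 0.43. That implies r of about 0.79 for a change contrast, about 0.76 with baseline adjustment, or averaging 12 weekly scores correlated at about 0.38. The documents give none of these, so the 95% is neither confirmed nor called wrong, and the point below does not depend on it.

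**Two-visit continuous outcome.** Each arm has 32 with both visits and 8 with baseline only; the covariance is treated as known.

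- Free baseline means: variance = 2[(1−r²)/32 + (1−r)²/40]. At r = 0.5: 2[0.02344 + 0.00625] = 0.0594, SE 0.244.
- Common baseline mean: variance = 2(1−r²)/32. At r = 0.5: 0.0469, SE 0.217. The 8 baseline-only participants do not affect this SE.

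| | r = 0.3 | r = 0.5 | r = 0.7 |
|---|---|---|---|
| SE, free means | 0.285 | 0.244 | 0.191 |
| SE, common mean | 0.238 | 0.217 | 0.179 |
| 95% CI half-width, free | 0.56 | 0.48 | 0.37 |
| 95% CI half-width, common | 0.47 | 0.42 | 0.35 |
| Variance ratio | 1.43 | 1.27 | 1.14 |
| Power at 0.6, free | 56% | 69% | 88% |
| Power at 0.6, common | 71% | 79% | 92% |

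The interval is 16 / 11 / 6% narrower. This does not depend on the 0.6. Ignoring baseline gives 67% power at every r. A completers-only change analysis, SE = sqrt(2·2(1−r)/32), gives 53 / 67 / 87%.

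**If 0.6 is in change-score SD.** The endpoint effect becomes 0.6·sqrt(2(1−r)) = 0.710 / 0.600 / 0.465. Power is 70 / 69 / 68% with free means, 85 / 79 / 74% with a common mean, and 81 / 67 / 46% ignoring baseline.

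**Higher r.** At 0.8 the SEs are 0.157 and 0.150, about 4% narrower, with power about 97% against 98%. At 0.9 the interval is about 2% narrower.

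**Weekly reports averaged.** Assume compound symmetry, 32 per arm and 12 × 0.8 = 9.6 reports per person, so v = (1 + 8.6r)/9.6. Variance factors are v ignoring baseline, v + 1 − 2r for change, and v − r² adjusted. Power is 98 / 90 / 80%, 78 / 90 / 99%, and over 99% respectively. The gain over ignoring baseline is about 2 / 9 / 20 points.

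**Simulation checks.** Two-visit trials with estimated covariance (20,000 trials) gave power of 54 / 67 / 87% for change and 69 / 77 / 91% constrained; type I error (10,000 trials) was 4.7–5.2% for all methods. A separate simulation of 32 completers per arm with five covariates fitted gave 50 to 68%, 62 to 75% and 84 to 89%.

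**The case against.** The strongest reply is that the plan is silent rather than wrong. The fixed effects are never written out, so the unconstrained model is an inference. On that reading baseline is already used, and a change contrast is a valid analysis of a randomised trial. If the means were in fact constrained, only a sentence is missing. All of this stands. It makes the matter one of efficiency, not validity.

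The size of the gain can also be challenged. r is assumed, and the largest gains come from the lowest r shown. If the plan's 95% power did rest on a two-visit change contrast, r would be near 0.79 and the gain only about one power point. That 95% may have another source, such as averaged weekly scores, so it does not fix r, but it is a fair warning against quoting the top of the range. Further, "an effective size of 0.6 improvement in symptom intensity score for the mVIP group over the control group" concerns an outcome reported weekly. Applying its 0.6 to a two-visit measure is illustrative, and only the interval widths avoid that borrowing. The weekly figures are for an average over follow-up; none is given for a week-12 contrast from the weekly data.

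Against a model of follow-up values alone, the gain can vanish if the five covariates already absorb the correlation. In simulation with total correlation 0.2–0.3 and covariate R² of 0.2, the SE moved by 1% or less. That is why r is defined here given the covariates.

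These points limit the size of the gain, not its direction: for 0 < r < 1, 1 − r² is below both 1 and 2(1 − r).

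**Conclusion.** The point holds, as an improvement that should be made; no bias or invalid test is shown. Neither covariate list contains the outcome's baseline value, and no common baseline mean is stated. Against free baseline means, the gain for a two-visit continuous outcome is a 16 / 11 / 6% narrower interval at r = 0.3 / 0.5 / 0.7, or 15 / 10 / 4 power points if 0.6 is read in endpoint SD. It shrinks to about 4% of SE at 0.8 and 2% at 0.9, and is about nil if the means were already constrained.

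This rests on an assumed r, equal SDs at the two visits and 32 completers per arm. It does not extend to the count or binary outcomes, or to any measure taken only at week 12. Confidence in the size is moderate, because r and the fitted mean structure are not documented.

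**What to change.** For each continuous outcome measured at baseline, state that baseline is a response in the mixed model with its mean constrained equal across arms, alongside the listed covariates. This keeps the mixed model, retains participants with only one visit, and costs no degree of freedom. Alternatively, use baseline as a covariate with post-baseline values only. That costs one degree of freedom and, with two visits, turns the mixed model into an ANCOVA.

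For two-visit binary and count outcomes, use the constrained form, or a single-row logistic or count regression on baseline without a random intercept. Describe odds ratios from either the random-intercept model or the baseline-adjusted regression as conditional.

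As a clarification, name the week-12 group difference as the estimate that tests the Aim 2 hypothesis in Specific Aims, since Data Analysis refers to the follow-up period as a whole.

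No new data are needed. Data Analysis is written in the past tense. If results are known, keep the reported result and add the adjusted estimate as a labelled additional analysis, which cannot replace it. If the baseline means were already constrained, a sentence saying so is enough.
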